In collaboration with the TOH mHealth team we are developing a tablet-based, patient-oriented, personalized risk communication application. The application leverages features of inclusive design, meaning that it will be useable even by older patients, who represent the largest demographic of surgical patients at TOH. Older individuals are often less tech-familiar, and may have visual and motor challenges that can make mobile technology use difficult. The application features simple and consistent design, large well-lit buttons that tolerate tremor, and simple language. The process will be applied in preoperative clinics at TOH, where patients will be asked to provide their personal health history through a series of questions already used on our TOH preoperative health screener. These values will then populate the NSQIP Universal Risk Calculator, which we have calibrated to TOH data, to generate personalized risks of mortality, serious complications, and hospital length of stay. These risk estimates will be communicated directly to the patient using absolute risk estimates represented pictorially (best practice for risk communication to patients). Risk estimates will also be provided to the patient's clinician. To facilitate shared discussion between patients and physicians, we will also ask the patient to identify up to 3 benefits they hope to achieve from surgery, and patients and clinicians will be provided with 3 evidence-based questions known to support Shared Decision Making (What are my options? What are the pros and cons of each option? How do I get the support to make the right decision for me?).

Study Design

The application will be evaluated using a controlled before-after study design. Patients will be recruited using standardized procedures, and process and outcome measures will be recorded using the same tools and methods in both study phases to decrease the risk of measurement and selection bias. The knowledge questionnaire will be completed prior to the clinic appointment, and repeated after. The primary outcome measure will be the change in knowledge from prior to the clinic appointment to after comparing the pre- and post-implementation groups. The satisfaction (patient experience) questionnaire will be administered after each patient's clinic appointment.

Outcomes

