Study population: We will recruit all consenting adults aged 18 or older seen in the Pre-Admission Unit prior to elective inpatient surgery at The Ottawa Hospital. Participants will be excluded if they are unable to communicate in English or French, or if they are unable to provide consent on their own due to cognitive impairment. Those scheduled for gastric bypass surgery will also be excluded due to significant differences in their pre-operative risk discussion.

During the post-implementation phase, patients will only be invited to participate in the study if the physician in clinic has provided consent for the study.

Sample Size: Sample sizes of 86 patients before and 86 after achieves 90% power to detect a minimally important difference in the mean improvement in knowledge test of 5 points (i.e., an improvement of 10 points after implementation versus 5 points before implementation) assuming a standard deviation for both groups of 10 and using a two-sided two-sample equal variance t-test at the 5% level of significance. 95 per group will allow for 10% dropout.

Data collection and management: Baseline and outcome data will be measured using various questionnaires (see study flow). Responses will be captured and stored via a RedCap data collection interface on a secure institutional research server. Length of stay data will be obtained by linking our data to our hospital Data Warehouse. All data will be stored in a privacy legislation-compliant manner.

Statistical analysis: Descriptive statistics will be used to compare recruitment rates and characteristics of patients in the pre- and post-implementation phases. Two-sample t-tests or chi-squared tests, as appropriate, will be used to examine statistical significance of differences. All outcomes will be expressed as biweekly means with graphical interpretation as a first step, using biweekly time series plots to detect the presence of any immediate versus gradual effects of intervention, and to examine the presence of trends, cyclical patterns, and outliers.

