Primary outcome (change in knowledge from before to after PAU appointment) will be analyzed using a linear segmented regression analysis of the biweekly means. The presence of autocorrelation will be assessed using Durbin-Watson tests, as well as visual inspection of residual plots. If autocorrelation is present, an autocorrelation parameter will be included in the model. The effect of the intervention will be reported as level and trend changes after the intervention, together with 95% confidence intervals. Patient-level linear regression analysis will be additionally conducted to adjust for potential differences

[name] – Research Proposal

A Patient-oriented risk communication tool to improve patient experience, knowledge and outcomes after elective surgery

[figure not shown]
in patient characteristics from pre- to post-implementation and to examine any predictors of outcomes or subgroup effects (e.g., by patient age, sex, multimorbidity status, and procedure). Subgroup analyses will be conducted by including the subgroup variables as well as their interaction with the intervention indicator into the regression models. All analyses will be conducted using SAS v. 9.4 with $\alpha = 0.05$ set for statistical significance.

Secondary patient-centered outcomes (patient experience, value, anxiety, acceptability) will be analyzed as described for the primary outcome. Normalizing transformations will be considered for patient-level analyses in case of substantial skewness, while ordinal logistic regression will be used for outcomes measured using a 5 point Likert scale.

Clinician-centered outcomes (likelihood to change management and acceptability, both measured using a 5-point scale) will be analyzed using biweekly summary measures using segmented autoregression as described for the primary outcome.

Feasibility and system outcomes will be described using frequencies and proportions and tabulated overall, and by implementation phase. Hospital length of stay will be analyzed using segmented linear regression as described for the primary outcome.

Study Flow: Questionnaires

[name] – Research Proposal

A Patient-oriented risk communication tool to improve patient experience, knowledge and outcomes after elective surgery

References

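### The 90% power is for a patient-level t-test; the named primary analysis, a segmented regression, has about 16% to 37% power for the same 5-point step, and no primary coefficient is named

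*Combined protocol and SAP*

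**What the plan says.** The Sample Size section of the combined protocol and SAP states: "Sample sizes of 86 patients before and 86 after achieves 90% power". The target is "a minimally important difference in the mean improvement in knowledge test of 5 points" (10 points after implementation against 5 before), with SD 10 in both phases, and the calculation is made "using a two-sided two-sample equal variance t-test at the 5% level of significance". It adds that "95 per group will allow for 10% dropout".

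The Statistical analysis section names a different test. The change in knowledge "will be analyzed using a linear segmented regression analysis of the biweekly means", and "The effect of the intervention will be reported as level and trend changes after the intervention", with 95% confidence intervals. An autocorrelation term is added if autocorrelation is found. Patient-level regression has an additional role: adjustment, predictors and subgroups. The t-tests mentioned earlier in that section follow the comparison of recruitment rates and patient characteristics, not the primary outcome.

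The Study Design section describes the primary outcome as the change "from prior to the clinic appointment to after comparing the pre- and post-implementation groups". That reads as a step between phases, but it does not name a model coefficient.

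**The concern.** Power belongs to a particular test of a particular parameter. The t-test compares two phase means. The level-change coefficient compares two fitted lines where they meet the interruption, which is the end of each line and so the place where it is least well determined. The same patients give much less information about that quantity, and the plan reports no power for it.

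The second gap is that two coefficients are reported with no order of priority, although the biweekly plots are introduced as "using biweekly time series plots to detect the presence of any immediate versus gradual effects of intervention". A step and a ramp load on different coefficients, so the choice can settle the result, and the plan allows it to be made after the data are seen.

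The practical risk is a null result read as coming from a 90%-powered study when the test performed had well under half that power.

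**Working it through.** **Inputs from the Sample Size section:** n = 86 evaluable per phase (95 recruited), difference 5, SD 10, two-sided alpha 0.05.

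**Assumptions, because the readable text gives no values:** K biweekly periods per phase, K = 3 to 43 (at n = 86, from about 29 down to 2 patients per mean); even accrual; independent errors; a pure 5-point step; a model with intercept, time, level change and trend change, the interruption lying midway between the last pre- and first post-implementation period.

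**Step 1. The plan's own figure.** SE = 10 × √(2/86) = 1.525. Noncentrality is 5/1.525 = 3.28 on 170 df, giving power 90.3% (92.9% at 95 per phase). The stated 90% reproduces.

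**Step 2. Standard error of the level change.** Each biweekly mean has variance 100K/86. Each fitted line is evaluated K/2 periods from the centre of its phase, and the sum of squares of time within a phase is K(K² − 1)/12. Adding the two phases:

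Var(level) = (200/86) × [1 + 3K²/(K² − 1)]

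The first factor is the variance of the two-sample contrast. The bracket is the price of estimating slopes: 4.375 at K = 3, falling to 4.002 at K = 43. It never drops below 4.

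**Step 3. Power** from the noncentral t with 2K − 4 df and noncentrality 5/SE:

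| K | SE (n = 86) | df | Power, n = 86 | Power, n = 95 | Difference detectable with 90% power, n = 86 | Mean 95% CI half-width, n = 86 |
|---|---|---|---|---|---|---|
| 3 | 3.190 | 2 | 15.7% | 16.8% | 21.7 | 12.1 |
| 4 | 3.125 | 4 | 23.6% | 25.5% | 13.7 | 8.2 |
| 6 | 3.082 | 8 | 29.9% | 32.4% | 11.4 | 6.9 |
| 12 | 3.058 | 20 | 34.4% | 37.3% | 10.4 | 6.3 |
| 43 | 3.051 | 82 | 36.7% | 39.9% | 10.0 | 6.1 |

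Simulation at n = 86 gave 15.7%, 23.8%, 29.9%, 34.4% and 36.6%. The half-widths are simulated averages; the t-test's is 3.0.

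**Step 4. Where the power goes.** On the same biweekly means at n = 86:
- A level-only model with no time term has 69% (K = 3) to 90% (K = 43), so averaging alone is not the main cause.
- Dropping only the trend-change term, with a common slope kept, gives 20% to 36.7%.
- A joint 2-df test of level and trend has 10.7% to 28.2%.
- Reaching 90% for the level change would take about 450 (K = 6) or 344 (K = 43) evaluable patients per phase.

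**Step 5. The unnamed coefficient (n = 86).** For an immediate 5-point step, the trend-change test rejects about 5% of the time. For a ramp starting from zero at the interruption and averaging 5 points over the post phase, the level-change test rejects about 5%, and the trend-change test has 18.7% (K = 3) to 46% (K = 43).

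**Step 6. Sensitivity (n = 86, K = 3 to 43).**
- Accrual weights falling 9 to 1 toward the interruption: 9.1% to 22.5%. Rising 1 to 9 toward it: 18.4% to 45.9%.
- AR(1) applied to the whole variance of the means, correlation treated as known: +0.4 gives 21% to 31%; −0.4 gives 17% to 68%; −0.6 gives 20% to 88% (91% at n = 95, K = 43).
- Sampling variance kept independent, with an AR(1) component of half that size added: +0.4 gives 13.2% to 21.6%; −0.6 gives 13.0% to 32.9%.

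**The case against.** The best defence is that the 90% is tied to the t-test in the very sentence that states it, that a mean shift between phases is plainly what the trialists intend, and that the patient-level regression will be reported anyway and could have power near 90%. The segmented model also guards against secular trend, and its wide intervals, promised for both coefficients, would show the imprecision. All of that is true. But it leaves the primary analysis with no power statement, and an intended step is not a named primary coefficient.

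A second line is that K, accrual and autocorrelation are not in the readable text, so the range cannot be anchored. That is correct, and it is why a range is given. More periods do not rescue the test, since the variance factor cannot fall below 4.

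Three objections to side figures stand:
- The strongly negative AR(1) results treat the sampling variance of otherwise independent patients as autocorrelated. With independent sampling noise and an added AR(1) component, power is lower, so the 88% and 91% figures should carry little weight.
- Accrual rising 1 to 9 at K = 43 implies 86/215 = 0.4 patients in the first fortnight, so 45.9% is not attainable in practice.
- The 5% figure for a gradual effect needs a ramp that is zero at the modelled interruption. A ramp that is zero at the first post period gives a level coefficient of −2.5 at K = 3.

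None of these restores 90% to the planned test.

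**Conclusion.** The concern holds. The 90% is right for a test the plan does not make primary. With the plan's own n, SD and effect, even accrual and independent errors, the level-change test has 15.7% to 36.7% power at 86 evaluable per phase, and 16.8% to 39.9% if all 95 are evaluable. Its expected interval half-width of about 6 to 12 points exceeds the 5-point minimally important difference. The exact value depends on the assumed number of periods, accrual and correlation, and these can move it either way. Only strongly negative autocorrelation applied to the whole variance of the means came near 90%. The absence of a named primary coefficient is a separate defect and does not depend on any of these assumptions.

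**What to change.** In the primary-outcome paragraph of the Statistical analysis section, name one primary coefficient, for example the level change, tested at two-sided 0.05, and label the other secondary. In the Sample Size section, replace the 90% claim with the power and detectable difference of that test under a stated number of biweekly periods per phase, accrual pattern and autocorrelation. If the 90% is kept, say that it applies only to an unadjusted patient-level comparison of phases.

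This is wording only, with no change to sample or data collection. The cost is a much less favourable stated power: about 16% to 40% for the level change with even accrual and independent errors.

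The sponsor could instead make a patient-level phase contrast without a time term primary and keep about 90%, but that gives up protection against secular trend. A linear drift of 2 points across the whole study puts the two phase means 1 point apart. On an SE of 1.525 with 170 df, that raises the type I error from 5% to 10%. This trade-off is the sponsor's to weigh and is not part of the required change.

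### No described analysis adjusts for calendar time and patient mix together, and the patient-level model does not say whether it includes time terms

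*Combined protocol and SAP*

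**What the plan says.** All references are to the Methods section of the combined protocol and SAP.

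- **Primary model (Statistical analysis).** The change in knowledge "will be analyzed using a linear segmented regression analysis of the biweekly means". On reporting: "The effect of the intervention will be reported as level and trend changes after the intervention, together with 95% confidence intervals". No patient covariate is named for this model.
- **Supplementary model (Statistical analysis).** "Patient-level linear regression analysis will be additionally conducted to adjust for potential differences" "in patient characteristics from pre- to post-implementation and to examine any predictors of outcomes or subgroup effects". No time term is listed, and none is ruled out.
- **Subgroups (Statistical analysis).** These are handled by "including the subgroup variables as well as their interaction with the intervention indicator into the regression models". No subgroup-by-time term is mentioned.
- **Trends (Statistical analysis).** Biweekly plots come first, among other things "to examine the presence of trends, cyclical patterns, and outliers".
- **Design (Study Design).** "The application will be evaluated using a controlled before-after study design". Only a pre- and a post-implementation group are described, with no concurrent control group.
- **Recruitment (Study population).** In the post-implementation phase, "patients will only be invited to participate in the study if the physician in clinic has provided consent for the study".
- **Secondary patient-centered outcomes** follow the approach set out for the primary outcome, so the same question applies to them.

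**The concern.** In a two-phase study without a concurrent control, two things can imitate an effect of the tool. Usual-care knowledge gain may drift over calendar time, or the patients may differ between phases. Both are plausible here. The plan itself looks for trends and expects differences in patient characteristics. The recruitment rule also changes at implementation, because physician consent becomes a condition of invitation.

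The segmented model answers the first threat and, as described, leaves the second open. The patient-level model answers the second and, as described, may leave the first open. If the two disagree, the plan gives no way to tell whether trend or patient mix is the reason. Two analysts could also fit the patient-level model with or without time terms, and both would be following the plan.

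**Working it through.** **Inputs from the documents (Sample Size):** 86 analysed per phase, SD 10, target difference 5 points, two-sided 5% t-test, 90% power.

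**Assumed, because the documents do not give them:** B biweekly periods per phase, uniform accrual, linear drift of s points per period, independent errors, and the size of any mix shift.

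**1. The plan's own figure.** SE of the difference = 10 × √(2/86) = 1.525. The exact noncentral t gives power 0.903 at 86 per group and 0.8999 at 85. The stated 86 is reproduced. This calculation contains no time term.

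**2. Patient-level model with phase but no time, no tool effect.** The phase midpoints lie B periods apart, so bias = s × B. Equivalently, it is half the total drift over the study. The false-positive rate is the noncentral t rejection probability with noncentrality bias/1.525 and 170 df.

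| s per period | B = 6: bias, false positives | B = 10: bias, false positives |
|---|---|---|
| 0.10 | 0.6, 7% | 1.0, 10% |
| 0.25 | 1.5, 16% | 2.5, 37% |
| 0.50 | 3.0, 50% | 5.0, 90% |

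Simulation of the middle case (s = 0.25, B = 10) gave 35-37%. With calendar time in the model, bias is near 0 and the false-positive rate about 5%.

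**3. Segmented model without covariates.** Suppose a binary characteristic worth 5 points moves from 40% to 60% of patients at implementation. The mean then steps by 5 × (0.60 − 0.40) = 1.0 point, and the level change takes up the whole step. Simulations gave 0.9 to 1.0. A patient-level segmented model with that covariate removes the bias. Its SE is also smaller than that of the biweekly-means model: 3.05 to 3.12 against 3.33 to 3.37 across simulations.

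**4. Subgroups.** With similar accrual timing in each subgroup:

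- Common drift adds s × B to the phase effect in every subgroup, so the interaction bias is s × B − s × B = 0. A simulation at s = 0.50, B = 10 gave −0.07 points and 5.2% false positives. Each within-subgroup phase effect still carries the full s × B.
- Drift in one subgroup only, s = 0.50 and B = 10, biases the interaction by 0.50 × 10 = 5.0 points. This is true of the phase-only model and also of a segmented model whose time terms are main effects only. Subgroup-by-time terms remove it.

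**5. Price in precision.** Adding calendar time and time since implementation multiplies the variance of the level change by 4.2 (B = 4) down to 4.0 (B = 24).

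- SE rises from 1.53 to between 3.05 and 3.13.
- Power for a 5-point level change at 86 per group falls from 90% to about 36-37%.
- Holding 90% power would need about 344 to 361 analysed per group.
- On biweekly means, with 2B − 4 residual df, power is about 24% (B = 4) to 36% (B = 24). The primary analysis therefore already pays this price.
- For two equal subgroups the phase-only interaction SE is 2 × 1.525 = 3.05. With subgroup-by-time terms it is about 2 × 3.06 = 6.1 (B = 10), and about 6.3 in simulation.

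**The case against.** **The primary analysis models time.** The segmented regression, with its autocorrelation check and biweekly plots, carries the main inference, and the patient-level model is additional. This stands. A reader might infer that the primary level and trend estimates are confounded by secular trend. They are not, for a linear trend.

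**The plan is silent on time terms; it does not exclude them.** A reader might infer that the patient-level model contains a phase indicator alone. The text does not say so. The intervention indicator appears only in the subgroup sentence, where it names the term being interacted, and that is compatible with a segmented model. The defect is under-specification, and the bias in the phase-only case is conditional on that reading.

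**Subgroup interactions do not absorb any trend whatever.** A reader might infer that every subgroup result is exposed. A common drift cancels from the interaction. Only drift that differs by subgroup biases it, and putting main-effect time terms in the model does not cure that. This objection stands in full and shapes the fix.

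**The drift is assumed.** The outcome is a within-patient change around one appointment, so drift in baseline knowledge need not carry over to it. The worst case in the table (0.50 over 20 periods) means 10 points of drift in total, twice the 5-point pre-implementation improvement assumed in the sample size. The smallest slope gives only 7-10% false positives. This is fair, and it limits the claim to a range. It does not explain how a disagreement between the two analyses would be read.

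**Time terms cost power.** True, and the cost must be stated. The phase-only model is closest to the t-test on which the trial was sized, which is a reason to keep it as a sensitivity analysis.

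**Conclusion.** The point holds in limited form. No described analysis contains both time terms and patient covariates, and the patient-level model is not specified well enough to show whether it keeps time.

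If it does not, the adjusted phase effect and the within-subgroup phase effects are biased by slope times phase length. For 6 to 10 periods per phase and slopes of 0.10 to 0.50, that is 0.6 to 5.0 points against a 5-point target. The middle case is 2.5 points. Separately, the segmented level change takes up any mix shift at implementation, about 1.0 point under the assumption used.

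These sizes rest on assumed drift, phase length and mix shift, with uniform accrual and independent errors. The documents do not show that any drift exists. The matter is worth correcting before analysis because the correction uses data already being collected, but it does not invalidate the primary analysis.

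**What to change.** Write out the patient-level model in the Statistical analysis section:

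- **Model.** Regress patient-level knowledge change on calendar time in biweekly units (zero at implementation), phase, time since implementation, and the planned patient characteristics, each named. Report the level and trend changes with 95% confidence intervals beside those from the biweekly-means model.
- **Subgroups.** Fit the subgroup-by-phase interaction in this model. Add subgroup-by-time terms wherever an interaction will be interpreted and trends may differ between subgroups. Label those results exploratory.
- **Sensitivity analysis.** Keep the phase-only adjusted model, labelled as not adjusted for time.
- **Secondary patient-centered outcomes.** State that the same specification applies, with the ordinal model where already planned.
- **Precision.** State that 86 per group was sized for a t-test without time terms, and give the expected power for the level change.

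The cost is SAP wording and one further SAS model, with no new data. The downside is precision: an SE of about 3.1 instead of 1.5 for the level change (power about 36-37% for 5 points), and roughly a doubling, from about 3.0 to 6.3, for an interaction with subgroup-by-time terms. The first of these is already carried by the primary segmented analysis.
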